^b Refer to Table 9.7.8.2.1 for laboratory assessments to be included, and to Table 9.7.8.4.1 for liver tests. LT assessment may be checked more frequently when ALT values are > ULN or ≥ 1.5x baseline value or based upon discussion between the Medical Monitor and the Investigator. Subjects with ALT > ULN or ≥ 1.5x baseline value during the study and either an alternative etiology considered or for further evaluation of the lab abnormality may undergo additional evaluations (eg, imaging studies including MRI or ultrasound, additional blood tests, and/or liver biopsy) at the discretion of the Investigator. Additional testing of FVIII and LTs during any study week may be performed if: (1) the ALT has increased to above ULN or increased by > 10 U/L from prior assessment; or (2) after a discussion between the Medical Monitor and the Investigator based on a review of subject data. If ALT values are stable over the course of several weeks, assessment of FVIII activity and ALT levels may be adjusted based on discussion between the Medical Monitor and the Investigator. During Years 2-5 of the Post-Infusion Follow-Up period, urine tests and blood, chemistry, and coagulation tests should be performed at the second Q12W visit each year and at every End of Year visit.

^cIncludes FVIII activity level (chromogenic substrate FVIII assay and one-stage clotting FVIII assay), Bethesda assay (with Nijmegen modification) for hFVIII inhibitor level, and coagulation exploratory assay. If a subject has used FVIII within 72 hours of a measurement day, all efforts should be made to obtain FVIII activity measurements when a 72-hour interval without FVIII use is achieved; the 72-hour wash-out period is only intended for subjects who have achieved FVIII ≥ 5 IU/dL at 16 weeks after BMN 270 infusion and who have not resumed FVIII replacement therapy. If FVIII levels are elevated or stable over the course of several weeks, assessment of FVIII activity may be adjusted based on discussion between the Medical Monitor and the Investigator. A D-dimer may be considered under circumstances in which FVIII activity levels are above the normal physiological range and/or if there is a concern for a venous thromboembolism. If a subject tests positive in the Bethesda assay (with Nijmegen modification) during Years 3-5, a fresh sample should be collected within 4 weeks of the initial visit that had a positive result.

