14.8 Determination of Sample Size

Approximately one hundred and thirty (130) subjects may be dosed in the study. The sample size for this study is based on clinical and statistical considerations in order to provide sufficient data to assess both safety and efficacy of BMN 270.

For the primary endpoint, a sample size of 130 will provide at least 95% power to demonstrate that the change in hFVIII activity during Weeks 49-52 from baseline is greater than 0, assuming an effect size of 0.6, using a one-sample t-test with a 2-sided significance level of 0.05. The effect size of 0.6 is assumed based on Study 270-201 data. In Study 270-201 cohort 6E13, the mean (SD) of FVIII activity (IU/dL) at Week 52 (based on median values in a 4-week window around Week 52) were estimated as 103.8 (62.4), with a 95% confidence interval for the mean of (46.1, 161.5). Using the lower limit of the confidence interval and assuming a baseline value of 1 (the largest value allowed per the study's inclusion/exclusion criteria), the effect size of change from baseline is approximately 0.7. For the sample size calculation, an effect size of 0.6 is assumed.

For the secondary endpoints, the analysis will be performed utilizing exogenous FVIII use and bleeding episode data from the 110 subjects whose baseline data will be prospectively collected for approximately 6 months in the non-interventional study 270-902, prior to their enrollment in Study 270-301. An analytic sample size of 110 will provide at least 95% power to demonstrate that the change in the annualized utilization (IU/kg) of exogenous FVIII replacement therapy in the efficacy evaluation period ("Week 5 to Last Visit") from the baseline is less than 0, assuming an effect size of 0.6 conservatively, using one-sample t-test with a 2-sided significance level of 0.05.

For the analytic sample size calculation of the second-ranked secondary endpoint, ABR, it is assumed that the pre- and post-BMN 270 infusion population mean ABRs are 3.5 and 1 respectively, and the distribution of ABRs is negative binomial distribution with a dispersion parameter of 2.2. Given the underlying negative binomial distributions, the standard deviations of the pre- and post-BMN 270 infusion ABRs are calculated as 7.8 and 1.8 respectively. The mean (SD) of the change from the pre- to post-BMN 270 infusion ABRs are calculated as -2.5 (8) assuming the correlation between pre- and post-BMN 270

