The first interim analysis was performed in May 2019 (data cut-off date: 30 April 2019) after 16 directly enrolled, HIV-negative subjects have completed the Week 26 visit. Based on the analysis results (p=0.001) and the totality of the data, the secondary interim analysis was deemed unnecessary (the test would be statistically significant at the pre-specified significance level of 0.001) and therefore never implemented. The 1-year analysis was performed in January 2021 (data cut-off date: 16 November 2020) after all subjects had been followed for 52 weeks post-BMN 270 infusion. Results from all pre-specified tests were statistically significant (p < 0.0001) at the alpha level of 0.0498 that was determined by the fallback procedure.

- If the first interim p-value ≤0.0002, the first interim result is declared significant and the 1-year analysis is carried out at the 0.05 level.
- If the first interim p-value >0.0002, the first interim result is not declared significant and the second interim analysis is carried out at 0.001 level. If the second interim p-value <=0.001, the second interim result is declared significant and the 1-year analysis is carried out at the 0.0498 level.
- If the second interim p-value >0.001, the interim results are not declared significant and the 1-year analysis is carried out at the 0.0488 level.

As specified in the 1-year analysis SAP (version 3.0, dated 17 December 2020), in the event that a 2-year final analysis is necessary, the testing procedure used in the 1-year analysis will be extended to the 2-year final analysis. That is, when all pre-specified tests are statistically significant at the 1-year analysis, the corresponding efficacy endpoints at 2 years will be tested in the same sequence under the same significance level.

Based on the fallback procedure and positive results from the 1-year analysis, the 2-year final analysis will be performed at the significance level of 0.0498 and the efficacy endpoints will be tested in the following hierarchical testing sequence:

1. For non-inferiority of BMN 270 versus FVIII prophylaxis in ABR with a NI margin of 3.5

Null hypothesis: post-baseline ABR – baseline ABR ≥ 3.5

2. For superiority of BMN 270 versus no treatment for severe hemophilia A in FVIII activity

Null hypothesis: FVIII activity at Week 104 – baseline FVIII activity ≤ 0

3. For superiority of BMN 270 versus FVIII prophylaxis in FVIII utilization

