25.3.6 Analysis Methods

Primary Efficacy Endpoint

The primary efficacy endpoint is change from baseline in ABR for treated bleeds.

The primary analysis of the primary efficacy endpoint will be based on the 270-902 Rollover Subjects. The baseline ABR under FVIII prophylaxis will be based on the data collected in 270-902. The ABR post-BMN 270 infusion will be based the data collected in the efficacy evaluation period, defined as Week 5 to each subject's last visit up to the analysis data cutoff date.

Change from baseline in ABR will first be tested for non-inferiority with a NI margin of 3.5 using the confidence interval approach. Assuming a t distribution, the 2-sid ed 95% confidence interval (CI) will be constructed for the mean change (post-baseline - baseline) in ABR. If the upper bound of the CI is less than 3.5, the non-inferiority of BMN 270 versus FVIII prophylaxis in ABR with this margin will be declared.

If non-inferiority is demonstrated, non-inferiority with smaller margins and superiority will be assessed using the same CI. The 2-sided p-value for superiority will be obtained through a one-sample t-test to test the null hypothesis that the change is 0 or greater.

A Wilcoxon signed-rank test and a negative binomial regress model will be used as sensitivity analyses for testing superiority in ABR.

First-Ranked Secondary Efficacy Endpoint

The first-ranked secondary efficacy endpoint is change from baseline in FVIII activity, as measured by chromogenic substrate assay, at Week 104 post-BMN 270 infusion.

The primary analysis of the first-ranked secondary efficacy endpoint will be based on the mITT population. The baseline FVIII activity value will be imputed as 1 IU/dL since there was no washout of severe hemophilia A subjects' usual FVIII prophylaxis (in order to avoid increasing the risk of bleeding) prior to BMN 270 infusion. FVIII activity values post BMN 270 infusion will be excluded from analysis if obtained within 72 hours (or 3 calendar days if time is not available) following an exogenous FVIII infusion. To reduce variation caused by random fluctuation, FVIII activity will be analyzed as the median of observed values in the

visit windows as defined in Section 20.1 of the 2-year analysis SAP. Missing data will be imputed as follows:

- Dropout missing
 - o For subjects who discontinue from the study early, missing FVIII activity values post-discontinuation will be imputed to be 0 IU/dL through the data cutoff date for the analysis.

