- Intermittent missing
 - o For subjects who continue on study, missing FVIII activity values (eg, due to a missed study visit) will be imputed to be the smaller of the last prior non-missing value and the next non-missing value. In rare cases where the next value is unavailable for a subject who did not drop out, the missing value will be imputed through linear extrapolation using the last two prior non-missing values.

A one-sample t-test will be used to test the null hypothesis that the change in FVIII activity from baseline to Week 104 (Week 104 - baseline) is 0 or less (ie, superiority when the null hypothesis is rejected). Summary of FVIII activity over time, including at Week 104, will be provided for descriptive purposes.

A complete case analysis (without missing data imputation), a mixed model for repeated measures (MMRM) approach, a last observation carried forward (LOCF) approach, and imputing missing data to be 0 IU/dL will be used as sensitivity analyses for testing superiority.

Additional details about the sensitivity analyses as well as the missing data imputation will be provided in the 2-year analysis SAP.

Second-Ranked Secondary Efficacy Endpoint

The second-ranked secondary efficacy endpoint is change from baseline in annualized utilization (IU/kg) of exogenous FVIII replacement therapy.

The primary analysis of the second-ranked secondary efficacy endpoint will be based on the 270-902 Rollover Subjects. The baseline FVIII utilization under FVIII prophylaxis will be based on the data collected in 270-902. The FVIII utilization post-BMN 270 infusion will be based the data collected in the efficacy evaluation period defined as Week 5 to each subject's last visit up to the analysis data cutoff date.

A one-sample t-test will be used to test the null hypothesis that the change from baseline in annualized FVIII utilization (post-baseline - baseline) is 0 or greater (ie, superiority when the null hypothesis is rejected). Change from baseline in annualized FVIII infusion rate (AFR)

Page **145**

number of exogenous FVIII infusions/year) will be analyzed similarly for descriptive purposes.

Safety Endpoints

Analysis of safety endpoints will be descriptive.

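### For subjects back on prophylaxis but still on study, the Week 104 FVIII rule extrapolates without bounds, allowing negative or never-observed values where a dropout scores 0

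*Protocol*

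**What the plan says.** Appendix 2 of the protocol makes change from baseline in FVIII activity at Week 104 the first-ranked secondary endpoint. Section 25.3.6 sets baseline at 1 IU/dL, analyses the mITT population with a one-sample t-test, and handles missing values as follows.

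- Exclusion: "FVIII activity values post BMN 270 infusion will be excluded from analysis if obtained within 72 hours" of an exogenous infusion, or 3 calendar days if the time is unknown.
- Dropouts: values after discontinuation are set to 0 IU/dL.
- On study, with a later valid value: the smaller of the previous and the next valid value.
- On study, with no later valid value: "the missing value will be imputed through linear extrapolation using the last two prior non-missing values". The section describes this situation as rare.

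Table 9.1.5 (footnote c) and Section 9.7.2.1 ask sites to seek a sample after 72 hours without FVIII, but "the 72-hour wash-out period is only intended for subjects who have achieved FVIII ≥ 5 IU/dL at 16 weeks after BMN 270 infusion". Subjects back on FVIII replacement are left out of it as well. Section 9.1 lets subjects with recurrent bleeding resume prophylaxis after discussion. Sections 9.1 and 12.7 keep treatment failures on study with fewer visits.

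Section 25.3.6 also plans complete-case, MMRM, LOCF and all-zero sensitivity analyses, and leaves further imputation detail to the 2-year SAP.

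**The concern.** Read together, these rules send a particular kind of subject to the extrapolation. Someone who has resumed prophylaxis and stays on study is not a dropout, so the zero rule does not reach him. Most of his samples fall inside the 72-hour exclusion, and sites are not expected to arrange a wash-out for him. Unless a later valid sample turns up, his Week 104 value comes from a straight line through two values that largely predate resumption. The example given for intermittent gaps, a missed visit, suggests that the rule was written with incidental gaps in mind. Here the gap is tied to the return to prophylaxis.

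A two-point slope carried over months amplifies ordinary fluctuation, which Section 9.7.2.1 itself calls common. It also does not match the peak, decline and steady state described in Section 7.3.1. With no bound, the result can be below zero or above anything measured in that subject. Two subjects with the same history are scored differently according to whether they left the study. What is at stake is the Week 104 mean change and its confidence interval, which readers will take as the 2-year durability estimate.

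**Working it through.** **1. The plan's own figure.** Section 14.8 states that "a sample size of 130 will provide at least 95% power" for FVIII activity at Weeks 49-52, with effect size 0.6, "using a one-sample t-test with a 2-sided significance level of 0.05". The noncentrality is 0.6 × √130 = 6.84, and power exceeds 0.9999. It still does at 0.0498, the level in Section 25.3.5 ("the 2-year final analysis will be performed at the significance level of 0.0498"). The statement holds with a wide margin. No power is stated for Week 104.

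**2. How often a resumed subject has a valid sample.** Section 7.3 gives usual prophylaxis as 2-3 infusions a week. Assuming even spacing:

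- twice weekly: 168/2 = 84 h between infusions, so (84 − 72)/84 = 14% of the time lies beyond 72 h;
- three times weekly: 168/3 = 56 h, so none does.

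Valid samples are therefore uncommon but possible.

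**3. What the rule returns.** With last valid values v1 at week w1 and v2 at week w2:

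value at Week 104 = v2 + (v2 − v1)/(w2 − w1) × (104 − w2)

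The activity values below are assumed. The 4-week spacing follows the full Year 2 schedule; the 12-week spacing follows the abbreviated schedule for treatment failures.

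| v1, v2 (IU/dL) | Weeks 72 and 76 | Weeks 64 and 76 | Dropout |
|---|---|---|---|
| 8, 11 | 11 + (3/4) × 28 = 32 | 11 + (3/12) × 28 = 18 | 0 |
| 11, 8 | 8 − (3/4) × 28 = −13 | 8 − (3/12) × 28 = 1 | 0 |
| 4, 6 | 6 + (2/4) × 28 = 20 | 6 + (2/12) × 28 = 10.7 | 0 |

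Earlier last values reach further: 8, 6 at Weeks 48 and 52 give 6 − (2/4) × 52 = −20, and 3, 4 give 4 + (1/4) × 52 = 17. From Week 76, the result is negative when the last fall exceeds v2 × 4/28 = 0.14 v2 (4-week spacing) or v2 × 12/28 = 0.43 v2 (12-week spacing).

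**4. Effect on the mean and the test.** The documents do not say how many subjects resumed, so this is illustrative. Take 130 subjects with normally distributed changes, SD 62.4 (the earlier cohort's SD in Section 14.8) and mean change 0.6 × 62.4 = 37.4. Replace 13 of them (10%), spread evenly over the distribution, by an imputed value minus the baseline of 1.

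| Imputed value for the 13 | Mean change, SD 62.4 | t | Mean change, SD 30 (assumed) | t |
|---|---|---|---|---|
| 0 | 33.7 | 6.59 | 16.1 | 6.56 |
| +17 | 35.4 | 7.02 | 17.8 | 7.41 |
| −20 | 31.7 | 6.05 | 14.1 | 5.40 |

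The shifts against zero are 13 × 17/130 = +1.7 and 13 × (−20)/130 = −2.0 IU/dL. Every two-sided p-value is below 0.000001.

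**The case against.** The strongest reply is that nothing decisive turns on this. The endpoint is secondary, its null value is a change of 0 or less, and the test has power to spare. ABR and FVIII utilization do not use the rule. The all-zero sensitivity analysis already applies to these subjects the score that one would want. The SAP, which prevails over the protocol on statistical methods, may add a floor. Exclusion depends on time since infusion rather than on prophylaxis status, and one later valid value brings in the smaller-of-two rule. Subjects dosed early have visits after Week 104 before the November 2021 cutoff. Wider visit spacing shrinks the examples.

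Most of that stands and limits the point. It does not remove it. The protocol fixes the primary rule and leaves only additional detail to the SAP; followed as written, the rule permits negative activity. Of the four sensitivity analyses, LOCF also carries pre-resumption values forward, complete-case drops these subjects, and MMRM treats their missingness as ignorable. Only the all-zero analysis addresses the problem, and the set is planned for testing superiority, not as the main estimate.

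A reader might infer that the rule favours the product. The documents do not support that: a falling slope, quite plausible given the decline in Section 7.3.1, counts against it. A reader might also infer that responder proportions are distorted. Appendix 2 plans none at Week 104; the 15, 25 and 30 IU/dL proportions in Section 14.2 concern Weeks 49-52 and a different imputation rule.

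**Conclusion.** The point holds in limited form. For subjects who resume prophylaxis, stay on study and have no valid value at or after Week 104, the primary rule can return an impossible or never-observed activity, while a dropout with the same history gets 0. The error can go either way. With 10% of subjects affected and extrapolated values of +17 or −20, the mean moves by about +1.7 or −2.0 IU/dL against scoring them 0. That size rests on the assumed number of resumed subjects, the assumed values and the visit spacing, none of which the documents settle. It also uses the planned 130 subjects as the mITT size.

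It would be wrong to read this as a threat to the superiority conclusion or to the primary ABR endpoint, or to assume that every resumed subject is affected. It is a defect in how a key secondary estimate is defined. It is worth correcting but does not by itself put the 2-year analysis in doubt.

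**What to change.** Change two sentences in Section 25.3.6 and carry them into the 2-year SAP.

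1. In the primary analysis, score an on-study subject who has resumed FVIII prophylaxis and has no valid value in or after the Week 104 window as a dropout is scored, at 0 IU/dL.
2. For any other on-study subject with no later valid value, bound the imputed value below at 0 and above at the last observed value. The smaller of the last two valid values is one simple way to do this. It is more generous than a bounded extrapolation when values are falling (11, 8 would give 8 instead of 0), so the choice should be stated.

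It would also help to report how many subjects fall under each imputation rule. The change is purely analytic: no visit, sample or treatment rule is touched. The cost is that the Week 104 mean may shift slightly, up or down.

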26 PROTOCOL AMENDMENT TEXT REVISIONS

The following table summarizes the revisions made to the protocol and relates the changes to the appropriate rationale (see pages 2-4). Added text is indicated by underlined font and deleted text is indicated by strikethrough font.

Section No./Title	Revision	Rationale
2/Synopsis (Study Rationale)	BMN 270 is being evaluated in clinical study 270-201, an ongoing first-in-human, phase 1/2 dose escalation study in subjects with severe HA designed to assess the safety and efficacy of BMN 270 at various dose levels (6E12 vg/kg, 2E13 vg/kg, 4E13 vg/kg, 6E13 vg/kg). Specifically, 270-201 explores the relationship of vector dose to the augmentation of residual FVIII activity and whether these levels are sufficient to alter the clinical phenotype. PreliminaryFour-year results from 270-201 and one-year results from 270-301 have demonstrated that following gene transfer, mean and median FVIII activity levels above 15% (15 IU/dL) and, in many cases, within the normal range for FVIII, is), as measured by a chromogenic substrate assay, are achievable with a doseand sustained following a single infusion of 4-6E13 vg/kg of BMN 270, with an acceptable safety profile (Pasi, 2017). Preliminary results from optional liver biopsies confirm dose-dependent pan-lobular and otherwise healthy liver transduction at 2.7-4.1 years.	12
2/Synopsis (Objectives)	 Assess the impact of BMN 270 on usage of exogenous FVIII replacement therapy from Week 5 to Week 52in the efficacy evaluation period (from Week 5 to last visit by the data cutoff for the 1-year analysis, hereafter referred to as "Week 5 to Last Visit") Assess the impact of BMN 270 on the number of bleeding episodes requiring exogenous FVIII replacement therapy from in the efficacy evaluation period ("Week 5 to Week 52Last Visit") The aforementioned study efficacy objectives were achieved through the pre-specified analysis at Week 52 ("1-year analysis") for the study, which was performed in January 2021 after all subjects had been followed for 52 weeks post-BMN 270 infusion (data cutoff date: 16 November 2020). Results from this analysis are intended to support regulatory submissions to EMA and other health authorities outside of FDA. The FDA has requested BioMarin to submit 2-year safety and efficacy data on all subjects in 270-301 to enable their benefit-risk assessment of BMN 270. To fulfill this regulatory requirement, Appendix 2 has been created to specify region-specific study objectives for the United States and the associated endpoints and analyses to achieve them. This analysis ("2-year analysis") will be performed after all subjects have completed the Week 104 visit or have withdrawn from the study. 	3,9
2/Synopsis (Study Design and Plan)	The final 1-year analysis for the study will be was performed after all subjects have had been followed for 52 weeks post-BMN 270 infusion. A separate 2-year analysis will also be performed per request from the FDA after all subjects have been followed for 104 weeks post-BMN 270 infusion. After the final analysis 1-year and the 2-year analyses, safety and efficacy will then continue to be assessed long-term in all subjects for a total of approximately 5 years.	3, 7, 9, 10, 12

Proprietary and Confidential

Section No./Title	Revision	Rationale
	Subjects who do not respond to BMN 270 treatment (ie, treatment failure, manifesting as either—failure to achieve FVIII activity ≥ 5 IU/dL by Week 52 or and inability to maintain independence from prophylactic FVIII replacement therapy due to joint bleeding episodes, in the judgment of the Investigator) may, at the Investigator's discretion and after discussion with the Medical Monitor or Sponsor-designated Data Monitor, follow an abbreviated visit schedule after Week 52 of the study by attending only the Q12W and End of Year visits during Years 2-5.	
	An optional liver biopsy will be performed as part of the liver biopsy substudy (in subjects who consent to do so) during Year 1 post-infusion, at or around Week 52, and/or during Years 2-5 following BMN 270 infusion. Subjects who consent to the liver biopsy will have additional assessments, including a liver ultrasound and FibroScan, and will receive prophylactic FVIII prior to the procedure, as if indicated in the judgment of the Investigator, to minimize the risk of bleeding. Additional liver biopsies may be performed as part of the substudy during Years 2-5 as clinically indicated.	
2/Synopsis (Criteria for Evaluation)	Secondary efficacy endpoints: • Change in the annualized utilization (IU/kg) of exogenous FVIII replacement therapy during in the efficacy evaluation period ("Week 5 to Week 52 post BMN 270 infusion Last Visit") from the baseline utilization of exogenous FVIII replacement therapy.	3
	• Change in the annualized number of bleeding episodes requiring exogenous FVIII replacement treatment (annualized bleeding rate, ABR) during therapy in the efficacy evaluation period ("Week 5 to Week 52 of the study post-BMN 270 infusionLast Visit") from the baseline ABR.	
2/Synopsis (Statistical Methods)	Sample Size For the secondary endpoints, the analyses will be performed utilizing exogenous FVIII use and bleeding episode data from the 110 subjects whose baseline data will be prospectively collected for approximately 6 months in the non-interventional study 270-902, prior to their enrollment in 270-301. An analytic sample size of 110 will provide at least 95% power to demonstrate that the change in the annualized utilization (IU/kg) of exogenous FVIII replacement therapy during in the efficacy evaluation period ("Week 5 to Week 52 post-BMN 270 infusion Last Visit") from baseline is less than 0, assuming an effect size of 0.6, using a one-sample t-test with a 2-sided significance level of 0.05.	3, 9, 12
	An analytic sample size of 110 will also have at least 95% power to demonstrate that the change in the annualized number of bleeding episodes requiring exogenous FVIII replacement treatment (ABR) during in the efficacy evaluation period ("Week 5 to Week 52 of the study post-BMN 270 infusion Last Visit") from the baseline ABR is less than 3.5 (non-inferiority margin), assuming the pre- and post-BMN 270 infusion population mean ABRs are 3.5 and 1 respectively, using a one-sample t-test with a 2-sided significance level of 0.05. Under the same assumptions, a sample	

Page 148

Section No./Title	Revision	Rationale
Section No./ Title	size of 110 will have approximately 90% power to demonstrate that the change is less than 0, ie, superiority of BMN 270 against FVIII prophylaxis. Analysis For the first-ranked secondary efficacy endpoint at Week 52 (ie, the change in the annualized utilization (IU/kg) of exogenous FVIII replacement therapy during Weeks in the efficacy evaluation period ("Week 5-52 post BMN 270 infusion from baseline), to Last Visit"), a one-sample t-test will be performed to test the null hypothesis that the change is 0 or greater against the alternative hypothesis that the change is less than 0. For the second-ranked secondary efficacy endpoint-at Week 52 (ie, the change in the annualized number of bleeding episodes requiring exogenous FVIII replacement treatment during Weeks 5-52 post BMN 270 infusion from baseline), in the efficacy evaluation period ("Week 5 to Last Visit"), a one-sample t-test will be performed to test for non-inferiority of BMN 270 against FVIII prophylaxis (ie, the baseline ABR calculated using subjects' data collected in 270-902) using a margin of 3.5, ie, to test the null hypothesis that the change is 3.5 or greater against the alternative hypothesis that the change is less than 3.5. If non-inferiority is demonstrated, the test for superiority of BMN 270 against FVIII prophylaxis will be performed.	Kationale
	The fallback procedure will be used to adjust for multiplicity of the two interim analyses at Week 26, and the final the 1-year analysis at Week 52, and the 2-year analysis at Week 104 (regardless of the interim analyses results, the study is planned to continue for a total of approximately 5 years upon the DMC's recommendation, and the final analysis will be performed at Week 52).). At the final 1-year analysis at Week 52 and the 2-year analysis at Week 104, the secondary efficacy endpoints will be tested hierarchically; the level of significance will be determined by the fallback procedure.	
7/Introduction	Hemophilia A (HA) is an X-linked recessive bleeding disorder that affects approximately 1 in 5,000 males (Nathwani, 1992, Baillieres Clin.Haematol.).Iorio 2019).	12
7.2/Ongoing Clinical Studies	 Study Ongoing clinical studies for BMN 270 include: 270-201 is an ongoing, a phase 1/2, dose-escalation study to assess the safety, tolerability, and efficacy of BMN 270 in patients with severe hemophilia A (HA) 270-203, a phase 2 study in patients with severe HA who have anti-AAV5 antibody titers 270-205, a phase 1/2 study in patients with severe HA who have active or prior FVIII <1 IU/dL). Subjects inhibitors 270-302, a phase 3 study in patients with severe HA who receive BMN 270 at the 4E13 vg/kg dose level 270-303, a phase 3 study in patients with severe HA who received a single BMN 270 infusion and are to be followed for safety and efficacy for up to 5 years. A total of 15 subjects have been enrolled at one of 4 dose levels (6E12, 2E13, 4E13, and at the 6E13 vg/kg), dose level along with prophylactic corticosteroids 	12

Page 149

Section No./Title	Revision	Rationale
7.3/Study Rationale	Preliminary Four-year results from 270-201 have demonstrated that following gene transfer, mean and median FVIII activity levels above 15% (15 IU/dL) and, in many cases, within the normal range for FVIII, is), as measured by a chromogenic substrate assay, are achievable with a doseand sustained following a single infusion of 4-6E13 vg/kg of BMN 270, with an acceptable safety profile (Pasi, 2017). Preliminary results from optional liver biopsies (in subjects receiving lower doses of BMN 270 in 270-201) confirm dose-dependent pan-lobular and otherwise healthy liver transduction at 2.7-4.1 years. For additional information on preliminary data in 270-201, refer to the current version of the Investigator's Brochure.	12
7.4/Summary of Overall Risks and Benefits	Transient, asymptomatic ALT elevation (grade 1 to 3 in severity) was observed in most subjects administered BMN 270 shortly after dosing, with no symptoms or sequelae suggestive of clinically significant hepatocyte injury or liver dysfunction. In almost all subjects, ALT elevations decreased quickly following corticosteroid treatment. There were differences in the use of corticosteroids across studies. Subjects in 270-201 received corticosteroids an average of 8 weeks earlier following BMN 270 infusion than the mITT population in 270-301, were more likely to avoid a significant decline in FVIII activity concurrently with an ALT elevation, and saw a more robust receivery of FVIII activity upon the first use of corticosteroids, than did the subjects in the mITT population in 270-301. Despite the clinical response to steroids, no associations between safety parameters (transient ALT rises), or efficacy as measured by FVIII activity levels were found to be temporally associated with anti-AAV5 antibody or cellular immune responses. Across the 6E13 vg/kg cohort of 270-201 and 270-301, subjects enrolled in 270-201 developed ALT elevation about 5.5 weeks later than subjects in 270-301, generally once the first course of corticosteroids was being tapered, and experienced lower peak elevations in ALT (75.7 U/L) than subjects in 270-301 (112.5 U/L). The difference in the ALT profile seen between the 6E13 vg/kg subjects in 270-201 and the subjects in 270-301 could be attributed to the difference in the protocol-specified corticosteroid regimens in place in those studies, including the early use of corticosteroids (ie, by Week 3 post-BMN 270 infusion). While the majority of ALT elevations responded approaches to managing or preventing ALT elevations, alternate non-steroidal systemic immunosuppressive agents have also been used to manage hepatic reactions where corticosteroids have proven to be ineffective or where high doses/and or prolonged exposure to corticosteroids have led to unwanted side effects. Overall, the literat	12

Proprietary and Confidential

Page	150
1 agc	120

Section No./Title	Revision	Rationale
8/Study Objectives	 Assess the impact of BMN 270 on usage of exogenous FVIII replacement therapy from Week 5 to Week 52in the efficacy evaluation period (from Week 5 to last visit by the data cutoff for the 1-year analysis, hereafter referred to as "Week 5 to Last Visit") Assess the impact of BMN 270 on the number of bleeding episodes requiring exogenous FVIII replacement therapy from in the efficacy evaluation period ("Week 5 to Week 52Last Visit") The aforementioned study efficacy objectives were achieved through the pre-specified analysis at Week 52 ("1-year analysis") for the study, which was performed in January 2021 after all subjects had been followed for 52 weeks post-BMN 270 infusion (data cutoff date: 16 November 2020). Results from this analysis are intended to support regulatory submissions to EMA and other health authorities outside of FDA. The FDA has requested BioMarin to submit 2-year safety and efficacy data on all subjects in 270-301 to enable their benefit-risk assessment of BMN 270. To fulfill this regulatory requirement, Appendix 2 has been created to specify region-specific study objectives for the United States and the associated endpoints and analyses to achieve them. This analysis ("2-year analysis") will be performed after all subjects have completed the Week 104 visit or have withdrawn 	3,9
9.1/Overall Study Design and Plan	The final 1-year analysis for the study will be was performed after all subjects have had been followed for 52 weeks post-BMN 270 infusion. A separate 2-year analysis will also be performed per request from the FDA after all subjects have been followed for 104 weeks post-BMN 270 infusion. After the final analysis 1-year and the 2-year analyses, safety and efficacy will then continue to be assessed long-term in all subjects for a total of approximately 5 years. Subjects who do not respond to BMN 270 treatment (ie, treatment failure, manifesting as either-failure to achieve FVIII activity ≥ 5 IU/dL by Week 52 erand inability to maintain independence from prophylactic FVIII replacement therapy due to joint bleeding episodes, in the judgment of the Investigator) may, at the Investigator's discretion and after discussion with the Medical Monitor or Sponsor-designated Data Monitor, follow an abbreviated visit schedule after Week 52 of the study by attending only the Q12W and End of Year visits during Years 2-5. An optional liver biopsy will be performed as part of the liver biopsy substudy (in subjects who consent to do so) during Year 1 post-infusion, at or around Week 52, and/or during Years 2-5 following BMN 270 infusion. Subjects who consent to the liver biopsy will have additional assessments, including a liver ultrasound and FibroScan, and will receive prophylactic FVIII prior to the procedure, as indicated in the judgment of the Investigator, to minimize the risk of bleeding. Additional liver biopsies may be performed as part of the substudy during Years 2-5 as clinically indicated.	3, 7, 9, 10, 12

Page	1	5	1
1 45	_	_	_

Section No./Title	Revision	Rationale
Table 9.1.5/Schedule of Events (Years 2-5)	Table 9.1.5 has been updated consistent with changes in the table footnotes and elsewhere in the protocol.	1, 5, 6, 7, 8, 12
Table 9.1.5 (footnotes)	ETV: Early Termination Visit **Complete physical examination should be performed at the End of Year visits; (genitourinary examination may be deferred); brief physical exam may be performed at other study visits. Weight should be recorded at the second Q12W visit each year and at every End of Year visit during Years 2-5. **Refer to Table 9.7.8.2.1 for laboratory assessments to be included, and to Table 9.7.8.3.1 for liver tests. LT< assessment may be monitored; hecked more or less frequently (and in particular when ALT values are > ULN or > 1.5x baseline value) or based onupon discussion between the Medical Monitor and the Investigator and review of subject data, but LTs will be monitored at least twice weekly during periods when a subject's ALT is > 3x ULN. Subjects with ALT > ULN or > 1.5x baseline value during the study and either an alternative etiology considered or for further evaluation of the lab abnormality may undergo additional evaluations (eg, imaging studies including MRI or ultrasound, additional blood tests, and/or liver biopsy) at the discretion of the Investigator. Additional betsing of FVIII and LTs during any study week may be performed if: (1) the ALT has increased to above ULN or increased by > 10 UL from prior assessment; (2) increases in ALT values from prior assessment are accompanied by declines in FVIII activity level; oror (2) after a discussion between the Medical Monitor and the Investigator based on a review of subject data. If FVIII levels and/orif ALT values are stable over the course of several weeks, assessment of FVIII activity and ALT levels may be adjusted based on discussion between the Medical Monitor and the Investigator. During Years 2-5 of the Post-Infusion Follow-Up period, urine tests and blood, chemistry, and coagulation tests should be performed at the second Q12W visit each year and at every End of Year visit. *Includes FVIII assay), Bethesda assay (with Nijmegen modification) for hFVIII within 72 hours of a measurement day, all efforts should be made to obtai	1, 5, 6, 7, 8, 12

Section No./Title	Revision	Rationale
	AAV5 TI Assay should be performed only at the end of the study (either the Year 5 End of Year Visit, or at the ETV for subjects who withdraw prior to the end of Year 5).	
